A total of two blood samples will be drawn over the course of the study - once at baseline and once after treatment has been completed. A trained, experienced nurse or phlebotomist will draw the blood. These blood samples will be processed by the VA laboratory to test for inflammatory markers, and the results will be uploaded to the participant's secure medical file. If they consent to storage of blood samples, the samples will later be used to examine genetic material.

If we are unable to complete labwork, overnight PSG or in-person cognitive tests due to VA restrictions or participant refusal as a result of COVID-19 concerns, we will not exclude these participants from the study.

TREATMENT

Our hypotheses will be tested in a randomized parallel groups design. Randomization will be based on type of treatment assignment: either to Cognitive Behavior Therapy for Insomnia (CBT-I) or Arousal-Based Therapy for Insomnia (ABT-I)(previously referred to as Desensitization Therapy for Insomnia) for the 6-week treatment phase.

CBT-I (SR & CT):

The CBT-I adopted in this trial will be based on our large-scale VA implementation of CBT-I and includes a published sleep self-help book, a published therapist guide, and the CBT-I therapist manual appended. It comprises both SR and CT as outlined below. The CBT-I therapy protocol consists of six sessions (an initial assessment and five treatment sessions). Treatment begins with a comprehensive sleep assessment and case conceptualization, which are used to guide selection and sequencing of CBT-I components. Treatment components include stimulus control, sleep restriction therapy, relaxation, and cognitive therapy. The final session focuses on maintenance of gains and relapse prevention.

Sleep Restriction Therapy (SR). The initial Time in Bed (TIB) prescription is calculated on the average total sleep time (TST) reported by subjects in their baseline sleep logs. Subsequently, the TIB prescription is determined using the formula: TIB = average TST. An additional treatment criterion is that prescribed initial time in bed should never be below 5 hours, even if the average total sleep time (TST) is very low (e.g., 3 hours). After one week, depending on subject's daily sleep logs and discussion with participant about tolerability, the therapist suggests a new TIB prescription. The

Title : Non-Pharmacological Treatments for Insomnia in Chronic Traumatic Brain Injury
Approval Period: 07/31/2024 - 07/31/2025

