initial TIB, retiring times and wake times are set with subject input to ensure tolerability. Daytime sleep will not be manipulated in SR treatment. Napping is neither prescribed nor proscribed. However, if subjects find themselves very sleepy (not just tired, but actually sleepy) they are advised to take a brief (15 to 30 minutes) nap to ensure their safety. These safety naps can be taken at any time because safety is always the most important consideration. Subjects are given additional rationale for the treatment constraints and suggestions for dealing with any difficulties they have in complying with their prescribed sleep schedules. Information on relevant elements of the science of sleep is included in explaining how the treatment works.

Cognitive Therapy (CT). The CT treatment module is designed to meet three general goals: 1) identification of dysfunctional sleep cognitions, 2) challenging their validity, and 3) replacing them with more adaptive substitutes. Several specific techniques designed to meet these goals are discussed in materials distributed to subjects. Systematic self-monitoring for identifying dysfunctional sleep cognitions will be a basic component of the treatment. Replacing inaccurate thoughts through cognitive restructuring involves the identification, evaluation, and modification of maladaptive thoughts. In the context of insomnia, the focus is on sleep-related thoughts that increase arousal, and therefore directly interfere with sleep. Basic concepts about CBT for chronic pain are included in training, for example, directly addressing hopelessness in relation to chronic pain that may interfere with sleep. Once sleep-incompatible thoughts are identified, dysfunctional ideas about the causes and consequences of insomnia and unreasonable expectations about normal sleep can be challenged in a nonjudgmental manner using scientifically based information about sleep and replacing them with more adaptive conceptions. Similar to SR, subjects in CT are given information about relevant elements of the science of sleep and healthy sleep practices.

Arousal-Based Therapy for Insomnia (ABT-I):

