The subjects assigned to the "Credible Control Therapy for Insomnia" (ABT-I) condition will receive a quasi-desensitization treatment presented as a means of eliminating the "conditioned arousal," which prolongs nocturnal awakenings. Therapists help each ABT-I recipient develop a chronological 8-item hierarchy of common activities he/she does on awakening at night (eg, opening eyes, clock watching). Therapists also help them develop 6 imaginal scenes of themselves engaged in neutral activities (e.g., reading the newspaper). Each session, ABT-I recipients are taught to pair neutral scenes with items on the 8-item hierarchy so, by the end of the sixth session, all hierarchy items have been practiced with therapist assistance. Each session, the exercise is tape recorded and the patient is given this tape locked in a player. The patients are told to practice their exercises at home once each day, no less than 2 hours before bedtime, but to avoid using the tape or exercise during sleep periods.

We will offer participants the option of completing therapy sessions via Telehealth and will aim to complete all treatment sessions via their chosen modality. If a participant needs to switch modalities

Title : Non-Pharmacological Treatments for Insomnia in Chronic Traumatic Brain Injury
Approval Period: 07/31/2024 - 07/31/2025

due to unforeseen circumstances (e.g. illness) we will accommodate this request.

FOLLOW UP

The complete package of outcome measures (including optional ambulatory PSG) will be repeated at the week 8 and six-month follow-up sessions. We will tell subjects that we expect the benefits of treatment to continue and/or improve with time and we will also encourage subjects to continue practicing the treatment instructions to maintain their progress.

b) Explain how the above research procedures are the least risky that can be performed consistent with sound research design.

There is little risk to the proposed procedures.

c) State if deception will be used. If so, provide the rationale and describe debriefing procedures. Since you will not be fully informing the participant in your consent process and form, complete an alteration of consent (in section 13). Submit a debriefing script (in section 16).

N/A

d) State if photo, audio or video recording will occur. Describe what will become of the photos or recording after use, e.g., shown at scientific meetings, erased. Describe the final disposition of the recordings.

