iii. The risks of the Commercially available drugs, reagents or chemicals. Information about risks can often be found in the package insert.

Not applicable.

iv. The risks of the Procedures to be performed. Include all investigational, non-investigational and non-invasive procedures (e.g., surgery, blood draws, treadmill tests).

Cognitive testing.

There are virtually no risks involved in the cognitive testing and psychosocial measurements other than the anxiety that can be associated with any test. Repeated evaluations of mood and mental status may be

Title : Non-Pharmacological Treatments for Insomnia in Chronic Traumatic Brain Injury
Approval Period: 07/31/2024 - 07/31/2025

slightly frustrating or produce fatigue and boredom.

Sleep Log and Questionnaires.

There are no harmful effects to filling out the sleep log and questionnaires, but some people may find answering the questionnaires annoying or boring.

Urine testing.

Urine testing involves no risk other than the bother involved.

EEG recording.

There is little risk to EEG recording. Participants may find the cap annoying or uncomfortable. If this occurs we will try to make them more comfortable, or stop the procedure if the participant requests.

Venipuncture.

Removal of blood by a needle and syringe poses a small risk of pain or bruising at the site of the needle stick, but this is temporary. Some people may experience fainting or dizziness, and there is also a slight risk of infection at the site of the needle stick.

Sleep treatments. It is possible that participants may become very sleepy under the Sleep Restriction part of the treatments. If this occurs, they will be advised to avoid driving, operating machinery, or doing activities that require close attention for the first few days of therapy.

v. The risks of the Radioisotopes/radiation-producing machines (e.g., X-rays, CT scans, fluoroscopy) and associated risks.

Not applicable.

vi. The risks of the Physical well-being.

See above procedures. No other risks to physical well-being are anticipated.

vii. The risks of the Psychological well-being.

From past experience, potential risk to participants is expected to be minimal. Specifically, questions asked that may be potentially distressing to the participants or may cause them to think about problems relating to them that may be anxiety-provoking or upsetting.

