A psychiatric screening will be performed to determine whether the participant meets inclusion and exclusion criteria for the study. From past experience, potential risk to participants is expected to be minimal. Specifically, questions asked may be potentially distressing to the participants or may cause them to think about problems relating to them that may be anxiety-provoking or upsetting. Patients who develop suicidal intent will be treated following established procedures at VAPAHCS.

Cognitive Testing.

There do not appear to be any risks associated with cognitive testing other than the commitment of significant time for participation. Some participants may experience anxiety during and after the cognitive testing.

Questionnaires.

There are virtually no risks involved in filling out our questionnaires, sleep-wake cycle questionnaires and sleep logs other than the time involved.

viii. The risks of the Economic well-being.

No risks to economic well-being are anticipated.

ix. The risks of the Social well-being.

No risks to social well-being are anticipated.

Overall evaluation of Risk.

Low - innocuous procedures such as phlebotomy, urine or stool collection, no therapeutic agent, or safe

Title : Non-Pharmacological Treatments for Insomnia in Chronic Traumatic Brain Injury
Approval Period: 07/31/2024 - 07/31/2025

therapeutic agent such as the use of an FDA approved drug or device.

b) If you are conducting international research, describe the qualifications/preparations that enable you to both estimate and minimize risks to participants. Provide an explanation as to why the research must be completed at this location and complete the [LINKFORINTERNATIONALREASEARCHFORM] International Research Form. If not applicable, enter N/A.

Not applicable.

c) Describe the planned procedures for protecting against and minimizing all potential risks. Include the means for monitoring to detect hazards to the participant (and/or to a potential fetus if applicable). Include steps to minimize risks to the confidentiality of identifiable information.

Suicidal thoughts.

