A Data and Safety Monitoring Plan (DSMP) is required for studies that present Medium or High risk to participants. (See Overall Evaluation of Risk above). If Low Risk, a DSMP may not be necessary. Multi-site Phase III clinical trials funded by NIH require the DSM Plan to have a Data Safety Monitoring Board or Committee (DSMC or DSMB). The FDA recommends that all multi-site clinical trials that involve interventions that have potential for greater than minimal risk to study participants also have a DSMB or DSMC.

The role of the DSMC or DSMB is to ensure the safety of participants by analyzing pooled data from all sites, and to oversee the validity and integrity of the data. Depending on the degree of risk and the complexity of the protocol, monitoring may be performed by an independent committee, a board (DSMC/DSMB), a sponsor's Data Safety Committee (DSC), a Medical Monitor, a sponsor's safety officer, or by the Protocol Director (PD).

Describe the following:

1. What type of data and/or events will be reviewed under the monitoring plan, e.g. adverse events, protocol deviations, aggregate data?

At each visit, participants will be asked about any adverse events which may have occurred since the last visit. Information about adverse events (including any injuries, illnesses, hospitalizations, etc.; this would include any adverse effects on sleep caused by study procedures) is collected at each visit by the interviewer. Any potentially serious problem is brought immediately to the Principal Investigator for review.

2. Identify who will be responsible for Data and Safety Monitoring for this study, e.g. Stanford Cancer Institute DSMC, an independent monitoring committee, the sponsor, Stanford investigators independent of the study, the PD, or other person(s).

The Protocol Director is the monitoring entity.

3. Provide the scope and composition of the monitoring board, committee, or safety monitor, e.g., information about each member's relevant experience or area of expertise. If the Monitor is the Stanford Cancer Center DSMC or the PD, enter N/A.

n/a

4. Confirm that you will report Serious Adverse Events (SAEs), Suspected Unexpected Serious Adverse Reactions (SUSARs), or Unanticipated Problems (UPs) to the person or committee monitoring the study in accordance with Sponsor requirements and FDA regulations.

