The Protocol Director will review all Adverse Events and Serious Adverse Events as soon as possible after the occurrence. SAEs are reported and forwarded to IRB as appropriate.

Title : Non-Pharmacological Treatments for Insomnia in Chronic Traumatic Brain Injury
Approval Period: 07/31/2024 - 07/31/2025

5. If applicable, how frequently will the Monitoring Committee meet? Will the Monitoring Committee provide written recommendations about continuing the study to the Sponsor and IRB?

Information about adverse events is collected at each visit by the interviewer. Any potentially serious problem is brought immediately to the Protocol Director. All data entered into the database is monitored by the senior research associate and the database manager.

6. Specify triggers or stopping rules that will dictate when the study will end, or when some action is required. If you specified this in Section 2g [Study Endpoints], earlier in this application enter 'See 2g'.

Criteria for discontinuation of a patient in the study will include an increase in bothersome nightmares for a week under treatment. We have not seen consistent reporting of nightmares with the proposed treatments, however that is always possible, hence again we would want to make sure that that occurred for at least a week before a patient was discontinued. Patients will be allowed to continue in the protocol after an SAE independent of treatment, e.g. hospitalization following a fall. All treatments are considered active and patients will be allowed to continue their treatment as a courtesy. However, data from such subjects will not be included in statistical analyses since such SAEs may affect sleep. Patients will not be restarted if their sleep deteriorates meeting the above criteria and they are discontinued from the protocol.

7. Indicate to whom the data and safety monitoring person, board, or committee will disseminate the outcome of the review(s), e.g., to the IRB, the study sponsor, the investigator, or other officials, as appropriate.

Serious Adverse Events are reported to the IRB using the standard reporting forms.

8. Select One:

The Protocol Director will be the only monitoring entity for this study.
 This protocol will utilize a board, committee, or safety monitor as identified in question #2 above.

10. Benefits

a) **Describe the potential benefit(s) to be gained by the participants or by the acquisition of important knowledge which may benefit future participants, etc.**

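### The only driving and machinery advice for participants made very sleepy by sleep restriction is limited to the opening days of therapy, although restriction runs longer.

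*Combined protocol and SAP*

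**What the plan says.** Section 9a.iv names the hazard under its entry on sleep treatments: "It is possible that participants may become very sleepy under the Sleep Restriction part of the treatments". If that happens, participants will be told to "avoid driving, operating machinery, or doing activities that require close attention for the first few days of therapy".

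Section 2a describes the restriction itself. Initial time in bed (TIB) is set to the average total sleep time from the baseline logs, with a floor of 5 hours. It is then revised: "After one week, depending on subject's daily sleep logs and discussion with participant about tolerability, the therapist suggests a new TIB prescription". This sits inside a 6-week treatment phase of six sessions, the first of which is an assessment. For participants who find themselves very sleepy, section 2a also recommends a nap of 15 to 30 minutes, without a calendar limit: "These safety naps can be taken at any time because safety is always the most important consideration". For the follow-up period it adds that "we will also encourage subjects to continue practicing the treatment instructions to maintain their progress".

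Section 9c of the form asks the investigators to "Describe the planned procedures for protecting against and minimizing all potential risks". The answer has entries on other topics but none on the sleep treatments. In section 9e, item 1 provides for adverse-event questions at each visit and notes that "this would include any adverse effects on sleep caused by study procedures". Item 6 states: "Criteria for discontinuation of a patient in the study will include an increase in bothersome nightmares for a week under treatment". It does not mention sleepiness.

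**The concern.** The driving advice carries two conditions: the participant is very sleepy, and therapy has only just begun. The first follows the hazard; the second follows the calendar. If restriction can still cause marked sleepiness after the opening days, the second condition removes the advice from someone who still meets the first.

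What is at stake is the safety of participants and of others on the road or near machinery. The protocol itself treats sleepiness under restriction as a reason not to drive. The entry criteria in section 8h add some weight: participants on stable CNS-active medication that may affect alertness can enter, and those at high risk of sleep apnea are referred for evaluation but not excluded. The documents do not show how far either raises the risk.

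**Working it through.** The protocol gives no figure to reproduce, so this is a comparison of stated durations and a search for any other text that would close the gap.

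**Step 1. How long each element lasts.**

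| Element | Stated duration | Where |
|---|---|---|
| Advice on driving, machinery and close-attention tasks | The opening few days of therapy, and only if very sleepy; number of days not defined | 9a.iv |
| First TIB prescription | One week (7 days), then a new prescription | 2a, Sleep Restriction Therapy |
| Treatment phase | 6 weeks (6 × 7 = 42 days) | 2a, Treatment |
| Safety naps when very sleepy | No limit stated | 2a, Sleep Restriction Therapy |
| Continued practice of instructions | Encouraged at follow-up | 2a, Follow up |

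On the ordinary meaning of a few days, the first TIB prescription alone outlasts the advice. After week 1 the text shows re-prescription, not an end to restriction, but it does not say whether TIB is tightened, held or relaxed. Continuation is therefore certain through week 1 and implied after it.

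**Step 2. Where the clock starts.** The limit is counted from the start of therapy, not from the start of restriction. Section 2a opens with an assessment session, and the assessment guides the order in which components are given. The opening days could pass before restriction begins.

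**Step 3. Whether other text closes the gap.**

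- Section 9c has seven headings: suicidal thoughts; cognitive testing; PSG and EEG; data; sleep log and questionnaires; telehealth; pre-screen surveys. Those on sleep treatments or sleepiness: 0 of 7.
- The discontinuation criteria in 9e item 6 name nightmares and do not mention sleepiness.
- The nap advice addresses the same state but not driving.
- The tolerability discussion (2a), the adverse-event questions (9e item 1) and the Epworth Sleepiness Scale (listed in section 16, schedule not shown) may detect sleepiness. None says what to advise about driving.

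Sentences in the supplied text that give driving or machinery advice: 1, the one in 9a.iv.

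**Step 4. Size.** The number of uncovered days cannot be computed, because the length of the advice is not defined. The number of participants affected cannot be computed either, because the documents do not say how often or when marked sleepiness occurs.

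**The case against.** The strongest objection is that section 9a is a risk summary for the IRB, not the script used with participants. The operative instructions are in the therapist manual, the consent form and the handouts, including one on sleep alteration listed in section 16. None of these is visible, so what participants are told about driving cannot be judged here. This stands as a limit on the claim, which covers the supplied text only. If those documents say more, the protocol sentence should still be brought into line with them.

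A second objection is that the closing phrase may only say when sleepiness is expected. The advice is triggered by a state, and section 8f describes transient worsening of sleep that should improve. That reading is possible. But the sentence attaches the time limit to the advice, 8f concerns sleep rather than daytime sleepiness, and a safety instruction should not depend on a generous reading.

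Third, sleepiness is managed in other ways: the 5-hour floor, TIB set to the participant's own average sleep time, schedules agreed with the participant, naps at any time, and adverse-event questions at every visit. These are real protections, and a participant who is sleepy in week 3 is not without help. None of them is advice about driving.

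Two smaller points are fair. The encouragement at follow-up is general and does not name sleep restriction, so it is weak evidence that restriction continues then. The absence of a heading in 9c also proves little by itself, since 9c does not mirror 9a item by item and has no heading for venipuncture or urine testing. The point rests on 9a.iv and 2a.

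**Conclusion.** The concern holds as a minor safety point. On its literal wording, the only driving and machinery advice in the supplied text lapses after the opening days of therapy, while the first TIB prescription runs a full week and is then renewed within a 6-week phase. A participant who remains very sleepy, or first becomes so, after that point is not covered.

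No event rate or duration can be attached to this, and it has no bearing on the sample size or the analysis. Confidence is medium. The conclusion assumes that the phrase limits the advice rather than describing expected timing, and that the unseen consent form, manual and handouts do not already give fuller advice. The practical benefit also depends on participants remaining to be treated: the Resources section expected completion by the end of 2023, the approval period runs to 07/31/2025, and the documents do not show treatment status.

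**What to change.** In section 9a.iv, replace the time limit with wording such as: *whenever they are very sleepy at any time during treatment or continued practice, and until the sleepiness has resolved*. Have therapists repeat the advice when sleep restriction starts and whenever TIB is changed. The repetition is a reminder only; the advice not to drive applies only while the participant is very sleepy. Copy the sentence into section 9c, and check that the consent form and CBT-I handouts match.

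The cost is one phrase, one line, a spoken reminder in sessions already planned, and a document check. The downside is that some participants will be advised not to drive for longer.

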- Be appropriately qualified to conduct the research and be trained in Human Research protection, ethical principles, regulations, policies and procedures
- Ensure all Stanford research personnel are adequately trained and supervised
- Ensure that the rights and welfare of participants are protected including privacy and confidentiality of data
- Ensure that, when de-identified materials are obtained for research purposes, no attempt will be made to re-identify them.
- Disclose to the appropriate entities any potential conflict of interest
- Report promptly any new information, modification, or unanticipated problems that raise risks to participants or others
- Apply relevant professional standards.

Any change in the research protocol must be submitted to the IRB for review prior to the implementation of such change. Any complications in participants or evidence of increase in the original estimate of risk should be reported at once to the IRB before continuing with the project. Inasmuch as the Institutional Review Board (IRB) includes faculty, staff, legal counsel, public members, and students, protocols should be written in language that can be understood by all Panel members. The investigators must inform the participants of any significant new knowledge obtained during the course of the research.

IRB approval of any project is for a maximum period of one year. For continuing projects and activities, it is the responsibility of the investigator(s) to resubmit the project to the IRB for review and re-approval prior to the end of the approval period. A Notice to Renew Protocol is sent to the Protocol Director 7 weeks prior to the expiration date of the protocol.

<https://stanfordmedicine.box.com/shared/static/qbsi8u8h47qsotxhdpuzz50xlrqa0sgo.pdf> Report promptly any new information, complaints, possibly serious and/or continuing noncompliance, or unanticipated problems involving risks to participants or others.

All data including signed consent form documents must be retained for a minimum of three years past the completion of the research. Additional requirements may be imposed by your funding agency, your department, or other entities. (Policy on Retention of and Access to Research Data, Research Policy Handbook, <http://doresearch.stanford.edu/policies/research-policy-handbook/conduct-research/retention-and-access-research-data>)

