APPROVAL LETTER/NOTICE NOTE: List all items (verbatim) that you want to be included in your approval letter (e.g., Amendment date, Investigator's Brochure version, consent form(s) version(s), advertisement name, etc.) in the box below.

By checking this box, I verify that I, as the Protocol Director (PD) responsible for this research protocol, have read and agree to abide by the above obligations, or that I have been delegated authority by the PD to certify that the PD has read and agrees to abide by the above obligations.

Statistical Analysis Plan

In testing Hypotheses 1 and 2, treatment response will be evaluated in terms of improvement in the Insomnia Severity Index (ISI) from baseline to end of the 6-week treatment.

Primary Hypothesis 1: Efficacy of CBT-I compared to a manualized active control condition, Arousal Based Therapy for Insomnia (ABT-I). To test the hypothesis that CBT-I will show efficacy for insomnia in TBI patients at the end of the 6-week treatment period, compared to the control condition (ABT-I) we will regress change in ISI on treatment (CBT-I versus ABT-I; 6 weeks vs. baseline). We will run analogous models to test for persistent treatment effects at the 16 and 24-week follow-up points. In each set of models the dependent variable will first be the change relative to baseline in our primary outcome measure of insomnia change defined by the ISI scores. We will covary for comorbid PTSD severity and amount of medication use (SSRIs) as required, if the frequency of such differs by treatment group.

Secondary Hypothesis 2: Moderators and Mediators of response. Our previous design separated Sleep Restriction (SR) and Cognitive Therapy (CT) components of CBT-I, however, we feel that although the design of the study has been changed, we can still gather some preliminary data on likely moderators and mediators of CBT-I, SR and CT while conducting the clinical trial and testing our Primary Hypothesis. Thus, we can still determine whether changes in potential moderators and mediators of SR and CT might also moderate or mediate the effects of the entire CBT-I package.

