effect in (3). We will compare the indirect effect to the total effect of treatment, estimated in (1), to determine how much of the total effect of treatment is accounted for by the mediator. Due to the non-normality of the estimates, percentile bootstrap confidence intervals for the mediator effects will be computed and their statistical significance assessed. We propose to use multiple imputation [99, 100] and an analyses based on total ISI change over the course of the study. Additional mediator analyses will be performed for relevant measures listed in Table 5.

Likelihood of Obtaining Useful Results. For our primary hypothesis we considered a target power of 80% with a two-tailed test at 5% significance in an Intention-to-Treat (ITT) analysis. We will require 60 subjects per group (for a total of 120 in the two groups) to detect a main effect of treatment group with an effect size that increases R-squared by 6% or more, with respect to the continuous outcome variable (ISI improvement). Thus we feel that the sample of 60 per group is adequate. Power analyses were computed using G*Power Version 3.1.9.2 [101].

Considerations Regarding Sleep Medication Changes During the Study. Tentatively, we would consider patients who required a sleep medication increase a treatment failure and they would be scored accordingly. We would interpret a decrease in medications a sign that therapy was working and assume that the ISI ratings would reflect a treatment success. We plan to monitor these assumptions with our statistical team and adjust our analyses appropriately.

Other analyses. The above is meant to be a brief outline of our analytic approach. Other analyses will be conducted including examination of secondary outcomes such as Quality of Life measures.

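### Protocol section 9e, question 6 removes randomised participants from the analyses after an unrelated SAE, while the SAP sets the primary test in an intention-to-treat analysis; both cannot hold

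*Combined protocol and SAP*

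**What the plan says.** Section 9e, question 6 of the protocol (triggers or stopping rules) first lets certain participants carry on: "Patients will be allowed to continue in the protocol after an SAE independent of treatment, e.g. hospitalization following a fall". It adds that "All treatments are considered active and patients will be allowed to continue their treatment as a courtesy". It then removes them from the results: "However, data from such subjects will not be included in statistical analyses since such SAEs may affect sleep". The removal is not limited to a secondary, per-protocol or sensitivity analysis, nor by when the SAE occurred.

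The SAP, under Likelihood of Obtaining Useful Results, says of the primary hypothesis: "we considered a target power of 80% with a two-tailed test at 5% significance in an Intention-to-Treat (ITT) analysis". That paragraph gives 60 per group, 120 in total. The SAP does not mention the SAE exclusion and defines no modified intention-to-treat set.

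On who assesses SAEs, section 9e, question 4 says: "The Protocol Director will review all Adverse Events and Serious Adverse Events as soon as possible after the occurrence". Question 2 of the same section names the Protocol Director as the monitoring entity. On the time span, Primary Hypothesis 1 in the SAP says: "We will run analogous models to test for persistent treatment effects at the 16 and 24-week follow-up points".

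**The concern.** Intention-to-treat keeps every randomised participant in the assigned arm whatever happens afterwards. An SAE during the protocol is a post-randomisation event, so a rule that deletes participants because of one cannot apply to an intention-to-treat primary analysis. Two analysts following these documents could analyse different people for the same primary test, and the choice could be made after outcomes are known.

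Three features make this more than a matter of wording.

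- **The trigger is a judgement.** Exclusion turns on whether the SAE was independent of treatment. No blinding to arm is described for that decision.
- **The judgement could differ by arm.** Section 9a lists marked sleepiness under sleep restriction as a risk. Section 2a includes sleep restriction in CBT-I and not in ABT-I. The protocol's own example of an independent event is a fall leading to hospital admission, and the independence of a fall may be easier to accept in one arm than in the other.
- **The stated reason concerns the outcome.** Participants are removed because the event may affect sleep, which is the domain the Insomnia Severity Index (ISI) measures.

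Read literally, an SAE after week 6 would also delete a week-6 ISI recorded before the event, although the stated reason cannot apply to that value.

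**Working it through.** **Side by side.** Section 9e, question 6: randomised, still in the protocol, SAE independent of treatment, data left out. SAP power paragraph: primary hypothesis, intention-to-treat, 60 per group. The participants described in the first are members of the second set by definition. The only missing-data method in the SAP, multiple imputation, appears in the mediator text and does not address this exclusion.

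**Inputs from the documents.** Two-sided alpha 0.05; target power 80%; R-squared increase 0.06; 120 randomised, 60 per arm; regression of ISI change on treatment. Section 8a plans to enrol 120, which equals the calculated sample size, so there is no allowance for exclusions.

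**The plan's own figure.**

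- f² = 0.06 / 0.94 = 0.0638, if no other covariate explains variance.
- For two equal arms, d = 2√f² = 0.505.
- Power comes from the noncentral F distribution with 1 and N − 2 degrees of freedom and noncentrality f² × N.
- At N = 120 the noncentrality is 7.66 and power is 78.4%.
- If other covariates explain about 4% of the variance (an assumption; residual 0.90), N = 120 gives 80.1%.

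The stated sample size is therefore close enough to its target and is not in dispute.

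**Power if the exclusion is applied.** Shares excluded are assumptions; f² = 0.0638 throughout.

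| Excluded | N analysed | Power |
|---|---|---|
| 0% | 120 | 78.4% |
| 5% | 114 | 76.2% |
| 10% | 108 | 73.9% |

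**Shift of the estimate against the all-randomised analysis.** Let p be the share excluded in an arm and k the number of SDs by which those excluded do worse than the rest of that arm. The mean of the whole arm lies p × k below the mean of those kept, so exclusion raises the arm mean by p × k. The treatment difference moves by

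shift = p(CBT-I) × k(CBT-I) − p(ABT-I) × k(ABT-I),

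with positive values favouring CBT-I. All p and k are assumed.

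| Excluded, CBT-I vs ABT-I | k | Shift (SD) | Share of d = 0.505 |
|---|---|---|---|
| 5% vs 5% | equal | 0 | 0% |
| 5% vs 2% | 0.5 to 1.0 in both | 0.03 × k = 0.015 to 0.03 | 3 to 6% |
| 8% vs 2% | 0.5 to 1.0 in both | 0.06 × k = 0.03 to 0.06 | 6 to 12% |
| 10% vs 0% (extreme) | 0.5 to 1.0 | 0.10 × k = 0.05 to 0.10 | 10 to 20% |
| 5% vs 5% | 1.0 vs 0.5 | 0.05 − 0.025 = 0.025 | 5% |

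Swapping the arms reverses the sign. The last row shows that equal exclusion rates alone do not remove the bias.

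**The case against.** The strongest reply has four parts.

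- **Intention-to-treat is named only once, in a sample-size paragraph.** The paragraph specifying the primary model names no analysis set, and the SAP calls itself a brief outline. This is true, but the power sentence is explicitly about the primary hypothesis and no other set is defined. The conflict stands.
- **The rule may cover only the six-week treatment phase.** The text speaks of continuing treatment, and no sessions remain after week 6. That narrower reading is possible. The text also speaks of continuing in the protocol and sets no time limit, so deletion of an earlier week-6 ISI follows from a literal reading but is not the only reading.
- **Blinded review may be described elsewhere.** The text does not say who decides that an SAE is independent. That it is the Protocol Director is an inference from the monitoring section. The SAP points to a section on blocking, and the attachment list names a grant submission; neither is in the text available. Blinded classification would lessen the bias risk but would not make the exclusion compatible with intention-to-treat.
- **The effect is small and assumed.** If events are truly independent of treatment and are classified correctly, exclusion rates should balance in expectation. The protocol rates risk as low and excludes unstable illness. This is fair: the case does not rest on a predicted large bias.

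**Conclusion.** The concern holds. As written, the primary analysis set is not determined: one section removes randomised participants whom the other must keep. If the exclusion is followed, the primary result is not an intention-to-treat result and observed ISI data are discarded on a post-randomisation judgement.

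The size cannot be derived from the documents. Under the assumed shares of 5 to 10% excluded, the power loss is about 2 to 4.5 percentage points. The bias ranges from nil to 0.10 SD in the extreme case, and its direction is unknown. The point needs correcting because of the contradiction in the primary analysis, whatever the eventual SAE count.

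**What to change.** Replace the exclusion sentence in section 9e, question 6 with: *All randomised participants are analysed in their assigned arm using all recorded ISI data, regardless of SAEs.* State the same set in the SAP under Primary Hypothesis 1. Keep the analysis without SAE participants as a sensitivity analysis only, which preserves the investigators' interest in sleep disturbed by intercurrent illness.

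This leaves the rule on continuing treatment after an SAE untouched. It does not settle two separate matters: the SAP's tentative scoring of sleep-medication increases as treatment failure, and the handling of participants with no week-6 ISI.

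The cost is one sentence in the protocol and one in the SAP, with no new data collection. The Obligations section requires IRB review first: "Any change in the research protocol must be submitted to the IRB for review prior to the implementation of such change". The change should be in place before the primary analysis is run. The downside is slightly noisier ISI values from participants who were ill during the study.
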